6.1.1.3 Visit 3 (Week 6)

The subject will return to the site for Visit 3. Procedures at Visit 3 will proceed as follows:

- Height and weight
- Vital signs (including systolic and diastolic blood pressure, radial pulse rate, and body temperature): performed after the subject has been in a sitting position for 3–5 minutes

- Collect seizure diary and review entries
- Record any AEs occurring since last visit and any that occur during this visit
- Record any changes in concomitant medications
- Blood draw for plasma PK of ataluren (0 hr, pre-dose, and 2 hr post-dose)
- Blood draw for plasma PK AED level assessment (0 hr, pre-dose)
- Dispense new seizure diary and review instructions for completion
- Review returned study drug and compliance
- Dispense masked study drug and review administration instructions
 - TID dosing 10 mg/kg, 10 mg/kg, 20 mg/kg (morning, midday, evening)
- Instruct subject to return in 6 weeks for Visit 4

6.1.1.4 Visit 4 (Week 12 [Beginning of 4-Week Washout])

The subject will return to the site for Visit 4. Visit 4 will proceed as follows:

- Physical examination
- Height and weight
- Vital signs (including systolic and diastolic blood pressure, radial pulse rate, and body temperature): performed after the subject has been in a sitting position for 3–5 minutes
- Collect seizure diary and review entries
- Record any AEs occurring since last visit and any that occur during this visit
- Record any changes in concomitant medications
- Blood draw for clinical laboratory evaluations
 - CBC, CMP, LFTs, BUN, creatinine, serum HCG
- Urinalysis
- Complete the following QOL assessments:
 - Behavior Assessment System for Children
 - VABS-II
 - QOLCE
- Review returned study drug and compliance
- Dispense new seizure diary and review instructions for completion
- No study drug will be dispensed at this visit
- Instruct subject to return in 4 weeks for Visit 5.

6.1.1.5 Treatment Period 2 - Visit 5 (Week 16 [Crossover Visit])

The subject will return to the site for Visit 5. Subjects will crossover and begin receiving masked study drug opposite of what they received during Treatment Period 1 (ie, subjects

previously receiving masked ataluren will now receive placebo and subjects previously receiving placebo will now receive ataluren). Visit 5 will proceed as follows:

- Physical examination
- Height and weight
- Vital signs (including systolic and diastolic blood pressure, radial pulse rate, and body temperature): performed after the subject has been in a sitting position for 3–5 minutes
- Collect seizure diary and review entries
- Record any AEs occurring since last visit and any that occur during this visit
- Record any changes in concomitant medications
- Blood draw for plasma PK of ataluren (0 hr, pre-dose)
- Blood draw for plasma PK AED level assessment (0 hr, pre-dose)
- Blood draw for clinical laboratory evaluations
 - CBC, CMP, LFTs, BUN, creatinine, serum HCG
- Urinalysis
- Complete the following QOL assessments:
 - Behavior Assessment System for Children
 - VABS-II
 - QOLCE
- Dispense new seizure diary and review instructions for completion
- Dispense masked study drug and review administration instructions
 - TID dosing 10 mg/kg, 10 mg/kg, 20 mg/kg (morning, midday, evening)
 - The first dose of study drug should be administered in the clinic *after* completion of all other assessments and procedures required at this visit.
- Instruct subject to return in 6 weeks for Visit 6

6.1.1.6 Visit 6 (Week 22)

The subject will return to the site for Visit 6. Visit 6 will proceed as follows:

- Height and weight
- Vital signs (including systolic and diastolic blood pressure, radial pulse rate, and body temperature): performed after the subject has been in a sitting position for 3–5 minutes
- Collect seizure diary and review entries
- Record any AEs occurring since last visit and any that occur during this visit
- Record any changes in concomitant medications
- Blood draw for plasma PK of ataluren (0 hr, pre-dose and 2 hr post-dose)
- Blood draw for plasma PK AED level assessment (0 hr, pre-dose)

- Dispense new seizure diary and review instructions for completion
- Review returned study drug and compliance
- Dispense masked study drug and review administration instructions
 - TID dosing 10 mg/kg, 10 mg/kg, 20 mg/kg (morning, midday, evening)
- Instruct subject to return in 6 weeks for Visit 7

6.1.1.7 Visit 7 (Week 28 – EOS Visit [or Early Termination Visit])/Start of Open-Label Extension Study

The subject will return to the site for Visit 7. This visit will be considered the EOS visit and should be completed for all subjects. Subjects should have taken their final dose of study drug the night before the clinic visit.

Additionally, any subject who discontinues early from the study should complete this visit.

Visit 7 will proceed as follows:

- Physical examination
- Height and weight
- Vital signs (including systolic and diastolic blood pressure, radial pulse rate, and body temperature): performed after the subject has been in a sitting position for 3–5 minutes
- Collect seizure diary and review entries
- Record any AEs occurring since last visit and any that occur during this visit
- Record any changes in concomitant medications
- Blood draw plasma PK for AED level assessment (0 hr, pre-dose)
- Complete the following QOL assessments:
 - Behavior Assessment System for Children
 - VABS-II
 - QOLCE
- Blood draw for clinical laboratory evaluations
 - CBC, CMP, LFTs, BUN, creatinine, serum HCG
- Urinalysis
- Review returned study drug and compliance
- If subject is enrolling in the open-label extension study, dispense new seizure diary and review instructions for completion
- No study drug will be dispensed at this visit if the subject is not enrolling in the open-label extension study.
- If the subject is enrolling in the open-label extension study, open-label study drug will be dispensed to the subject.

6.1.2 Open-Label Extension Study

6.1.2.1 Visit 8 (Week 52)

The subject will return to the site for Visit 8 (Week 52), of the open-label extension study.

Visit 8 (Week 52) will proceed as follows:

- Physical examination
- Height and weight
- Vital signs (including systolic and diastolic blood pressure, radial pulse rate, and body temperature): performed after the subject has been in a sitting position for 3–5 minutes
- Collect seizure diary and review entries
- Review returned study drug and compliance
- Record any AEs occurring since last visit and any that occur during this visit
- Record any changes in concomitant medications
- Blood draw plasma PK for AED level assessment
- Blood draw for clinical laboratory evaluations
 - CBC, CMP, LFTs, BUN, creatinine, serum HCG
- Urinalysis
- Complete the following QOL assessments:
 - Behavior Assessment System for Children
 - VABS-II
 - QOLCE
- Open-label study drug will be dispensed at this visit.
- Dispense new seizure diary and review instructions for completion.

6.1.2.2 Visit 9 (Week 76)

The subject will return to the site for Visit 9 (Week 76).

Visit 9 (Week 76) will proceed as follows:

- Physical examination
- Height and weight
- Vital signs (including systolic and diastolic blood pressure, radial pulse rate, and body temperature): performed after the subject has been in a sitting position for 3–5 minutes
- Collect seizure diary and review entries
- Review returned study drug and compliance
- Record any AEs occurring since last visit and any that occur during this visit
- Record any changes in concomitant medications
- Blood draw for clinical laboratory evaluations

- CBC, CMP, LFTs, BUN, creatinine, serum HCG
- Urinalysis
- Open-label study drug will be dispensed at this visit.
- Dispense new seizure diary and review instructions for completion.

6.1.2.3 Visit 10 (Week 100)

The subject will return to the site for Visit 10 (Week 100).

Visit 10 (Week 100) will proceed as follows:

- Physical examination
- Height and weight
- Vital signs (including systolic and diastolic blood pressure, radial pulse rate, and body temperature): performed after the subject has been in a sitting position for 3–5 minutes
- Collect seizure diary and review entries
- Review returned study drug and compliance
- Record any AEs occurring since last visit and any that occur during this visit
- Record any changes in concomitant medications
- Blood draw for clinical laboratory evaluations
 - CBC, CMP, LFTs, BUN, creatinine, serum HCG
- Urinalysis
- Open-label study drug will be dispensed at this visit.
- Dispense new seizure diary and review instructions for completion.

6.1.2.4 Visit 11 (Week 124)

The subject will return to the site for Visit 11 (Week 124)

Visit 11 (Week 124) will proceed as follows:

- Physical examination
- Height and weight
- Vital signs (including systolic and diastolic blood pressure, radial pulse rate, and body temperature): performed after the subject has been in a sitting position for 3–5 minutes
- Collect seizure diary and review entries
- Review returned study drug and compliance
- Record any AEs occurring since last visit and any that occur during this visit
- Record any changes in concomitant medications
- Blood draw plasma PK for AED level assessment
- Blood draw for clinical laboratory evaluations
 - CBC, CMP, LFTs, BUN, creatinine, serum HCG

- Urinalysis
- Complete the following QOL assessments:
 - Behavior Assessment System for Children
 - VABS-II
 - QOLCE
- For subjects that want to continue on study medication, open-label study drug will be dispensed at this visit.
- For subjects that do not want to continue, study drug will not be dispensed at this visit and subjects will return in 4 weeks for the final follow up.
- Dispense new seizure diary if subject continues to visit 12 and review instructions for completion.

6.1.2.5 Visit 12 (Week 128 [Follow-up Visit])

The Follow-up visit is to occur 4 weeks after the last dose of study drug, regardless of whether the subject discontinues prematurely or completes the EOS visit and/or the open-label extension.

Visit 12 will proceed as follows:

- Physical examination
- Height and weight
- Vital signs (including systolic and diastolic blood pressure, radial pulse rate, and body temperature): performed after the subject has been in a sitting position for 3–5 minutes
- Collect seizure diary and review entries
- Record any AEs occurring since last visit and any that occur during this visit
- Record any changes in concomitant medications.

6.2 PK for AED and Ataluren

Antiepileptic drug plasma PK will be assessed at 0 hr (pre-dose of AED). The AED levels will be done prior to the subject taking the medication (trough level). Antiepileptic drug levels will be analyzed by NYU outpatient labs and/or MedTox laboratories.

Ataluren plasma PK will be assessed at 0 hr (pre-dose) at Week 16 and at 0 hr (pre-dose) and 2 hr post-dose at Weeks 6 and 22. Ataluren plasma samples will be shipped to InVentiv Bioanalytical Facility, [name], for analysis and levels.

6.3 Blood Collection Summary

Assuming a subject completes the study, the maximum amount of blood to be drawn at a visit is approximately 8 to 20 mL (depending on the number of AEDs the subject is taking and blood withdrawn for the ataluren PK assessment). The total amount of blood to be drawn over the entire study period (including the Screening Visit, Treatment Period 1, Treatment Period 2, and EOS) is approximately 70 mL (depending on the number of AEDs the subject is taking as well as blood samples collected for the ataluren PK assessment).

6.4 Blood for Analysis of Pharmacokinetics

6.4.1 Ataluren Plasma Concentration

Blood for trough ataluren concentrations will be collected at 0 hr (pre-dose) at Visit 5/Week 16 and at 0 hr (pre-dose) and 2 hr post-dose at Visit 3/Week 6 and Visit 6/Week 22. Reference the Instruction Manual for handling ataluren in human PK samples for collection, processing, and shipping details. Samples will be stored at the bioanalytical laboratory for analysis of ataluren parent drug using a validated high-performance liquid chromatography with tandem mass spectrometry method. Thereafter, samples may be retained for potential follow-up analyses of ataluren metabolites.

7 STATISTICS

7.1 Sample Size Determination

The original study was not powered for statistical testing since the primary objective is to characterize the safety profile of ataluren in subjects with CDKL5 or Dravet syndrome resulting from a nonsense mutation. Eighteen subjects (10 with CDKL5 syndrome and 8 with Dravet syndrome) was planned to be included in this study. At the time of protocol amendment, 7 subjects Dravet syndrome have been randomized and 8 subjects with Dravet syndrome have been randomized. Enrolment has been stopped. The number of subjects randomized will provide an initial assessment on the efficacy for subjects with CDKL5 syndrome and with Dravet syndrome.

The number of subjects enrolled in the open-label extension study will be determined by the number of subjects who complete the initial study and remain eligible to participate in the extension study.

7.2 Randomization

Eighteen subjects (10 with CDKL5 syndrome and 8 with Dravet syndrome) will be enrolled. Within each disorder group, subjects will be randomized in a 1:1 ratio to 1 of 2 possible treatment assignments during Treatment Period 1:

- Placebo
- Ataluren (10, 10, 20 mg/kg/day)

After the completion of Treatment Period 1 and a 4-week Washout Period, subjects will crossover and begin receiving masked study drug opposite of what they received during Treatment Period 1 (ie, subjects previously receiving masked ataluren will now receive placebo and subjects previously receiving placebo will now receive ataluren).

7.3 Populations for Analyses

Intent-to-Treat (ITT) Population - The ITT Population will contain all randomized subjects.

7.4 Efficacy Endpoint Definitions

7.4.1 Seizures

Based on observational studies of subjects with CDKL5 and Dravet syndrome in other drug studies, mean seizure frequency of 70 with a standard deviation of 65 has been estimated. From the epilepsy literature ([Cramer 1999](#)), a clinically meaningful difference will be a $\geq 20\%$ reduction in seizure frequency over placebo.

Seizure activity will be assessed based on ILAE criteria for the following:

- Motor seizure including tonic-clonic seizures, hemiconvulsive seizures, drop attacks, tonic seizures, focal motor seizures.
- Staring seizure is an absence seizure or a complex partial seizure.
- Myoclonic seizure is the persistence or disappearance seizure.
- Episode of status epilepticus: a convulsive state lasting longer than 10 minutes.

Baseline total number of seizures/emergency room visits/hospitalizations is defined as the total number of seizures/emergency room visits/hospitalizations during the 4-week Screening Period (Week -4 to Week 0 [Day 1]).

7.4.2 Clinical and Adaptive Measures of Personality and Behavior

Assessment of clinical and adaptive measures of personality and behavior will be made using the Behavior Assessment System for Children (Third Edition). This is a screening system for measuring behavioral and emotional strengths and weaknesses. It will be conducted by the Principal Investigator or Clinical Research Nurse/Coordinator.

7.4.2.1 Adaptive Level of Behavioral Function

Adaptive level of behavioral function will be measured by the VABS-II ([Sparrow 2005](#)). The assessment is used to evaluate the child's ability to adapt to practical, everyday skills that are required to function and meet environmental demands. The assessment will be conducted by the Principal Investigator or Clinical Research Nurse/Coordinator.

7.4.2.2 Quality of Life

Quality of life will be assessed by the QOLCE ([Sabaz 2003](#)). This questionnaire is used to evaluate the QOL of these children living with epilepsy. It will be distributed to the caregivers to complete.

7.5 Statistical Analyses

The confidence interval (CI) for the proportion, if presented, will be computed using normal approximation, if the number of the events is at least 5. Otherwise, CI using an exact method will be provided. For safety summaries, CI will not be presented, unless specified otherwise. Summary statistics will be analyzed within each disorder group.

All analyses will be performed using Statistical Analysis System (SAS[®]), Version 9.0 or higher.

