1.5 Study Design

[figure not shown]
Crossover designs are usually statistically efficient and thus require fewer subjects. Additionally, the influence of confounding covariates is reduced because each crossover subject serves as his or her own control. A 12-week treatment period with ataluren provides sufficient time to assess changes in the subject's seizure activity and QOL while still allowing appropriate monitoring of the subject. Due to the lack of effective alternative treatment, subjects and their parents/legal guardians will be motivated to participate in this study. Therefore, we expect a low dropout rate.

The study to be conducted is a Phase 2 interventional study which includes the following: Screening (Week -4 to Week 0/Day 1), Treatment Period 1 (Week 0/Day 1 to Week 12), Washout Period (Week 12 to Week 16), crossover to Treatment Period 2 (Week 16 to Week 28), and a Follow-up visit after 4 weeks. Subjects who complete this study may be eligible to enroll in a 96-week open-label extension study (Week 28 to Week 124). A Follow-up visit is to occur 4 weeks after the last dose of study drug for all subjects, regardless of whether a subject discontinues prematurely or completes the End-of-Study (EOS) visit and/or the open-label extension. For subjects who enroll in the extension study, Follow-up is scheduled to occur at Week 128. The opportunity to enroll in the extension study will be explained to subjects during the initial study informed consent by the site investigator; subjects enrolling in the extension study do not need to re-consent.

The treatment period in this study ends at Week 124 (Visit 11). However, for subjects that want to continue on study medication beyond Week 124, PTC Therapeutics will continue to supply drug. All subsequent visits will be standard of care and any blood work will be at the discretion of the investigator. A follow up visit for subjects who do not want to continue will be scheduled 4 weeks following the last dose. Access to study drug will continue until commercial availability of ataluren for this indication or until a positive risk-benefit assessment in this indication is not demonstrated whichever is first.

The study design is shown in Figure 2. The Schedule of Events is provided in Table 1.

Figure 2: Study Design

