7.5.3.1 Discontinuation of Study Therapy

The ITT Population will be used to summarize discontinuation from study drug as indicated in Section 7 as well as the reason for the premature termination of study drug. The proportion of subjects who discontinue study drug will be summarized using point estimates and 95% CI.

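### The confidence interval rule for proportions looks only at the number of events, so in groups of 7 and 8 it can give an upper limit above 100% or an interval of zero width (minor)

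*Combined protocol and SAP*

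**What the plan says.** Section 7.5 (Statistical Analyses) sets one rule for any proportion given a confidence interval. The interval "will be computed using normal approximation, if the number of the events is at least 5". For smaller counts, "Otherwise, CI using an exact method will be provided". There is no condition on non-events or on group size, no formula, and no mention of truncating limits at 0 or 100%. The same section says "Summary statistics will be analyzed within each disorder group", and that safety summaries carry no interval by default.

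The one proportion for which an interval is required is in Section 7.5.3.1: "The proportion of subjects who discontinue study drug will be summarized using point estimates and 95% CI".

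Section 7.1 gives the group sizes. The plan was for 10 CDKL5 and 8 Dravet subjects. At the amendment, "7 subjects Dravet syndrome have been randomized and 8 subjects with Dravet syndrome have been randomized", and "Enrolment has been stopped". The sentence names Dravet twice, so one label is evidently a slip. I take 7 and 8 as one disorder each; which is which does not matter here.

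Section 1.5 adds, without a figure, "Therefore, we expect a low dropout rate".

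**The concern.** The normal approximation to a binomial proportion fails near 100% just as it does near 0%, so a minimum count has to apply to non-events as well as events. The plan checks one side only. If 5 were required of each, n would have to be at least 5 + 5 = 10, and the approximation could never be used in a group of 7 or 8. As written, it applies exactly where such a group has few or no non-events.

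The result would be a published interval that is either impossible (upper limit above 100%) or falsely precise (no width at all, from 7 or 8 children). The discontinuation table would be affected, and so would any other proportion for which an interval is later presented under the same rule.

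**Working it through.** The documents state no interval or coverage figure, so there is nothing of the plan's own to reproduce. I applied the rule itself.

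**Inputs.** Rule and within-disorder reporting: Section 7.5. Group sizes 7 and 8, pooled 15: Section 7.1. Level 95%: Section 7.5.3.1. Assumed: two-sided interval, Wald form, no continuity correction, no truncation.

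**Formulas.** Wald: p ± 1.96·√(p(1−p)/n), with p = x/n. Exact: Clopper-Pearson limits from beta quantiles.

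**Two cases in full.**
- 5/7: p = 0.714; √(0.714 × 0.286 / 7) = 0.171; half-width 0.335; limits 38.0 to 104.9%.
- 7/8: p = 0.875; √(0.875 × 0.125 / 8) = 0.117; half-width 0.229; limits 64.6 to 110.4%.

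**Every count that reaches the normal branch in a single group.**

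| Count | Plan's rule (Wald) | Exact |
|---|---|---|
| 5/7 | 38.0 to 104.9% | 29.0 to 96.3% |
| 6/7 | 59.8 to 111.6% | 42.1 to 99.6% |
| 7/7 | 100 to 100% | 59.0 to 100% |
| 5/8 | 29.0 to 96.0% | 24.5 to 91.5% |
| 6/8 | 45.0 to 105.0% | 34.9 to 96.8% |
| 7/8 | 64.6 to 110.4% | 47.3 to 99.7% |
| 8/8 | 100 to 100% | 63.1 to 100% |

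All three triggered counts fail at n=7, and three of four at n=8. If the groups are pooled, 5/15 to 11/15 stay in range and the fault starts at 12/15 (upper limit 100.2%).

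**Chance of a faulty interval.** This is P(X ≥ 5) for n=7, P(X ≥ 6) for n=8 and P(X ≥ 12) for n=15. The documents give no discontinuation rate, so a range is assumed.

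| True rate | n=7 | n=8 | n=15 |
|---|---|---|---|
| 10% | 0.02% | 0.002% | <0.001% |
| 20% | 0.5% | 0.1% | <0.001% |
| 30% | 2.9% | 1.1% | 0.01% |
| 50% | 23% | 14% | 1.8% |

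**Coverage of the plan's rule** (exact below 5 events, Wald from 5), summed over the binomial distribution for n = 7, 8 and 15, nominal 95%:
- true proportion 10 to 30%: 97.1 to 99.8%
- 40 to 70%: 88.5 to 98.1%
- 80%: 78.6 to 82.2%
- 90%: 51.9 to 79.2%

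The exact interval covers 96.5 to 99.7% over the same grid (10 to 90% in steps of 10).

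**The case against.** The strongest objection is practical reach. The general rule applies only where an interval is presented, safety summaries have none by default, and Section 7.7 names only a Hodges-Lehmann interval, which is not for a proportion. That leaves discontinuation, where at least 5 of 7 or 6 of 8 children would have to stop study drug. At true rates up to 30% the rule does not undercover, and the poor coverage figures belong to rates of 80 to 90% that nothing in the documents supports. All of this stands, and it is why the point is minor. It does not remove the point: Section 7.5.3.1 makes the discontinuation interval mandatory, no dropout figure is given, and the section does not say whether the extension counts, so a higher cumulative rate cannot be excluded.

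Second, the plan does not say Wald. A Wilson interval also rests on a normal approximation and has neither defect. That is a fair reading but not the ordinary one, and the plan should not leave it open.

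Third, limits might be cut off at 100%. The plan does not say so, and truncation would leave 7/7 and 8/8 with zero width and would not restore coverage. A continuity correction of 1/(2n) would remove the zero width but push every triggered count in groups of 7 and 8 above 100% (5/8, for example, to 102.3%).

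Fourth, Section 7.5.3.1 refers to the ITT population, which could mean all 15 together. Pooling makes the fault rarer but does not remove it.

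**Conclusion.** The concern holds, as a minor one. Followed as written, the rule gives an impossible or zero-width interval at six of the seven counts that trigger the normal approximation in groups of 7 and 8. How likely that is depends on a discontinuation rate the documents do not give: small if dropout is low, appreciable if about half of a group stops study drug. The primary Wilcoxon and Hodges-Lehmann analysis does not use the rule. The conclusion assumes the Wald form, no truncation, and one disorder in each of the two groups. The arithmetic is certain under those assumptions; the practical weight is modest.

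**What to change.** In Section 7.5, delete the normal-approximation branch and state that every proportion presented with an interval gets the exact (Clopper-Pearson) interval, whatever the event count. The plan already uses an exact method below 5 events, so this is one sentence and one software option. It removes all out-of-range and zero-width results.

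The cost is somewhat wider intervals: 7/8 goes from 46 points (64.6 to 110.4%) to 52 points (47.3 to 99.7%), and pooled 10/15 from 48 points (42.8 to 90.5%) to 50 points (38.4 to 88.2%). The exact interval also covers more than 95%.

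Two alternatives would work. Wilson is acceptable, though its coverage falls to 91.5% at n=15 with a true proportion of 30 or 70%. Requiring at least 5 events and at least 5 non-events also cures the groups of 7 and 8, but only because the normal branch is then never used in them; the exact method throughout is simpler. Section 7.5.3.1 should also say whether discontinuation is reported by disorder, pooled, or both.
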